3.6.6.7 Photography of Skin Lesions

Photographs of skin lesions in DM patients only will be requested at screening but are not required for study participation. For patients who have skin lesions at screening, up to two representative lesions will be chosen by the investigator and serial photographs will be taken. One of the two lesions will be the lesion selected for the punch skin biopsy. Preferably, the photographs will be taken prior to the punch skin biopsy. For patients who do not have skin lesions at screening but subsequently develop lesions during the study, up to two lesions will be selected by the investigators and serial photographs will be taken during the rest of the study period. See Appendix I for instructions.

3.6.7 Correlative Studies

Correlative studies include collection of serum for assessment of autoantibodies and proteomics, collection of serum for IFN- α assays and other exploratory research, peripheral blood for flow cytometry, and muscle and skin biopsies. It is preferred that the follow-up for the open muscle biopsy is done on the contralateral muscle, and the follow-up punch skin biopsy is done in close proximity to the first biopsy.

Other correlative studies include collection of whole blood and muscle for type I interferon inducible gene expression and whole blood for analysis of DNA. Collection of blood for DNA analysis is voluntary, and patients must sign a separate informed consent form (Informed Consent Form for Collection of Blood Samples for DNA Analysis) in order for this test to be done. Patients who do not wish to have the DNA test done will still be eligible for the study.

3.6.7.1 Serum for Exploratory Research and Storage

Serum samples will be obtained and analyzed for exploratory research, including IFN- α assays, analyses of autoantibodies, and proteomics. Analysis of the serum proteome will be carried out through the use of a large multiplex quantitative platform for known analytes. Exploratory studies for novel analytes may be carried out by 2-dimensional electrophoresis followed by high performance liquid chromatography and mass spectrophotometry or other methods.

Aliquots of serum may be frozen and stored for additional exploratory studies based on research findings.

3.6.7.2 Serum for Autoantibody Testing

As part of the disease activity and damage assessments, autoantibodies including ANA, anti-SSA, anti-RNP, anti-Jo-1, anti-SRP, and anti-Mi-2 antibodies will be measured in serum samples.

3.6.7.3 Open Muscle Biopsies

Open muscle biopsies will be performed at visits indicated in Table 4. The initial open muscle biopsy will be performed on an involved muscle within 28 days prior to Study Day 0. Involved muscle is defined as having a muscle strength of 4 to 4-/5 as assessed by MMT. The repeated open muscle biopsy will be performed on a muscle that was noted to be involved on Study Day

0. If involved on Study Day 0, the contralateral muscle is the preferred site of the repeated biopsy. The open muscle biopsy samples collected during the trial will undergo histopathological grading and IHC analysis of cellular infiltrates, including dendritic cell subtypes, B cells, and T cells. Additionally, gene expression will be analyzed, and changes in IFN-inducible protein levels within muscle specimens will be assessed by IHC methods.

3.6.7.4 Skin Biopsies

Skin lesions in patients with DM will be selected by the investigator for punch biopsy. Analysis of type 1 IFN-inducible gene expression, histologic evaluations, and IHC analyses of the punch skin biopsy samples will be performed. The procedure is requested but not required for study participation.

3.6.7.5 Flow Cytometry

Peripheral blood samples will be collected for flow cytometry at selected sites in North America. Phenotypic analysis of blood cell populations will be conducted using multicolor flow cytometry with a panel of markers specific to cell surface and intracellular markers. The panel of markers covers all major peripheral blood cell subsets including B cells, monocytes, neutrophils, blood dendritic cells, and various types of T cells. The longitudinal follow-up of the patients will help to determine if any changes in the characteristics of the cellular populations are correlated to the study drug and if the changes are associated with clinical effects.

3.6.7.6 Effects on Type I IFN-Inducible Gene Expression

The pharmacodynamics of MEDI-545 will be studied through analyses of its effects on type 1 IFN-inducible gene expression in whole blood, muscle, and skin. The levels of mRNA for type I IFN-inducible genes will be measured using genomic tests. PCR assay on selected panel of genes may be used to confirm the results. The analysis in whole blood is performed using Affymetrix whole genome expression array and taqMan-based assay on selected panel of genes. In muscle and skin, immunohistochemical methods will be used to stain for a pre-selected panel of genes that will allow further assessment of the pathogenesis of inflammatory muscle disease. Subsequent studies will be dependent upon the results obtained from our initial analyses.

3.6.7.7 DNA Analysis

To investigate characteristics associated with patients' clinical response and safety, one blood sample (8.5 mL) will be collected on Study Day 14 and frozen at -80°C for DNA sample preparation. The sample will be frozen and stored until used in exploratory analyses. The specific tests include analyses for DNA single nucleotide polymorphisms (SNPs) and microsatellite or short tandem repeats to further evaluate particular genes involved in the signaling pathway relevant to type I interferons.

The collection of blood for DNA analysis is optional. The completion of a separate informed consent form (Informed Consent Form for DNA Analysis) is requested but not required for participation in the trial. Patients who do not wish to have the DNA test done will still be

eligible for the study. Patients who elect to have the DNA test done may, at any time before the end of the study, request that the blood collected for DNA analysis be destroyed.

All specimen and patient identifiers must be removed from the DNA blood samples such that under no circumstances can the DNA blood samples be linked back to a specific patient. In most cases, this will require that DNA blood samples have current labeling removed and the tubes relabeled. Special labeling capable of adhering to frozen tubes must be used. If it is not possible to remove the original labeling, then it must be determined whether the DNA blood samples can go through a freeze thaw and be re-aliquoted in order to maintain confidentiality. All re-labeled DNA blood samples must be cross referenced to the original demographics in a secure database to ensure that only appropriate laboratory personnel have access to these data. A special release must be obtained prior to use of specified DNA blood samples.

3.7 Completion of Study, Discontinuation of Study, and Loss to Follow-up

Patients will be considered to have completed the study if they were followed up through Study Day 350. It should be specified on the case report form whether or not the patient completed the study follow-up procedures through Study Day 350.

If a patient discontinues his or her participation in the study, the patient will return to the study site and complete the Study Discontinuation Visit evaluations. If the patient discontinues prior to Study Day 98, the patient should complete the evaluations scheduled for Study Day 98. If the patient discontinues after Study Day 98 and prior to Study Day 196, the patient should complete the evaluations scheduled for Study Day 196. If the patient discontinues after Study Day 196, the evaluations scheduled for Study Day 350 must be completed. If a particular assessment has been performed within 2 weeks before the discontinuation visit, it need not be repeated.

Patients will be considered lost to follow-up only if no contact has been established by the time the study is completed such that there is insufficient information to determine the patient's status at Study Day 350. Investigators or qualified designees should document attempts to re-establish contact with missing patients throughout the study period. If contact with a missing patient is re-established, follow-up should resume according to the protocol.

Patients who participate in this study may have the option of terminating early to enter the MI-CP212 study. This includes both MEDI-545 and placebo patients, but excludes patients who discontinued from previous MEDI-545 clinical studies for safety reasons. Patients must complete the treatment period and follow up through study Day 266 of this study to participate in MI-CP212. Patients will be considered terminated from this study upon signing the MI-CP212 informed consent form between study Day 266 and Day 350. If possible, patients should complete the Study Day 350 evaluations on their last study visit. If a particular assessment has been performed within 2 weeks before the discontinuation visit, it need not be repeated.

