Patients who participate in this study may have the option of entering a long-term safety study (MI-CP212). This includes both MEDI-545 and placebo patients, but excludes patients who discontinued from previous MEDI-545 clinical studies for safety reasons. Patients must complete the treatment period and follow up through Day 266 of this study to participate in MI-CP212. Patients must also qualify for the long-term safety study (following written informed consent), as per the MI-CP212 protocol inclusion and exclusion criteria. If patients qualify, they will receive open-label MEDI-545. Patients may be treated for approximately 3 years and may be followed for an additional 3 months following the last dose of IV MEDI-545.

PATIENT POPULATION:

The patients in the study must be adults with probable or definite DM or PM according to the Bohan and Peter criteria (Bohan, 1975) and have active disease. Patients will either have low/undetectable or high level of expression of mRNA for type I IFN-inducible genes in whole blood or muscle at the time of screening. High level of expression, defined as a median fold

overexpression of the top 25 type I IFN inducible genes of 4-fold or greater, is referred to as gene signature positive, and low/undetectable level of expression is defined as gene signature negative.

The patient will be counseled by an investigator (physician) or qualified designee who will address the questions and concerns of the patient and secure written informed consent for participation in the study. Written informed consent will be obtained prior to conducting study procedures or administration of study drug.

TREATMENT:

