Patients are considered evaluable if they receive the first 4 doses of study drug (MEDI-545 or placebo) and complete the required evaluations, or if they discontinue study drug administration at any time for safety reasons. Nonevaluable patients may be replaced to maintain a size of at least 8 patients per dose cohort. Data from all patients will be included in safety analyses. A dose cohort may be expanded by up to 4 additional patients (for a maximum of 20 additional patients in total) if eligible patients are in screening at the time 8 patients have been randomized into the dose cohort.

Study drug administration will start on Study Day 0 and continue through Study Day 182. At the end of the treatment period, patients will be followed for 24 weeks, through Study Day 350. Safety parameters including assessments of AEs and SAEs will be assessed at every study visit from the signing of the informed consent through Study Day 350. Disease activity will be assessed throughout the treatment period and during follow-up. Patient evaluations are described in Table 4 and Table 5.

Decisions regarding dose escalation will be made by the Medical Monitor based on the review of all cumulative, blinded safety information which includes the safety data through Study Day 42 from the first 8 evaluable patients in each of the preceding lower dose cohorts (Section 4.9).

The study schema is described in Figure 1.

[figure not shown]

Figure 1 Study schematic

Patients who participate in this study may have the option of entering a long-term safety study (MI-CP212). This includes both MEDI-545 and placebo patients, but excludes patients who discontinued from previous MEDI-545 clinical studies for safety reasons. Patients must complete the treatment period and follow up through Day 266 of this study to participate in MI-CP212. Patients must also qualify for the long-term safety study (following written informed consent), as per the MI-CP212 protocol inclusion and exclusion criteria. If patients qualify, they will receive open-label MEDI-545. Patients may be treated for approximately 3 years and may be followed for an additional 3 months following the last dose of IV MEDI-545.

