3.1.2 Exclusion Criteria

Patients must have *none* of the following criteria:

1. Receipt of MEDI-545 in any previous clinical study or prior randomization into the trial;
2. History of allergy or reaction to any component of the study drug formulation;
3. Inclusion body myositis, cancer-associated myositis, myositis associated with another connective tissue disease, environmentally-associated myositis, or drug-related myopathy;
4. A history of or a family history of noninflammatory myopathy, scapular winging, atrophy, or hypertrophy of the calf muscles;
5. Receiving prednisone > 35 mg/day (or an equivalent dose of another corticosteroid) within 14 days before Study Day 0;
6. Receiving the following dosages of medications within 28 days before Study Day 0: hydroxychloroquine > 600 mg/day, mycophenolate mofetil > 3 g/day, methotrexate > 25 mg/week, azathioprine > 3 mg/kg/day, or any dose of cyclophosphamide, cyclosporine, or thalidomide;
7. Have received fluctuating doses of antimalarials, mycophenolate mofetil, methotrexate, leflunomide, or azathioprine within 28 days before Study Day 0 or fluctuating doses of corticosteroids within 14 days before Study Day 0;
8. Have received leflunomide > 20 mg/day in the 6 months prior to Study Day 0.
9. Treatment with any investigational drug therapy within 28 days before Study Day 0 or biologic therapies (eg, rituximab) within 30 days or 5 half-lives of the biologic agent, whichever is longer, before Study Day 0;
10. In the investigator's opinion, evidence of clinically significant active infection, including ongoing, chronic infection, within 28 days before Study Day 0;
11. A history of severe viral infection as judged by the investigators, including severe infections of either CMV or the herpes family such as disseminated herpes, herpes encephalitis, ophthalmic herpes;
12. Herpes zoster \leq 3 months prior to Study Day 0;
13. Evidence of infection with hepatitis B or C virus or HIV-1 or HIV-2, or active infection with hepatitis A, as determined by results of testing at screening;
14. Vaccination with live attenuated viruses within 28 days before Study Day 0;
15. Pregnancy (sexually active women, unless surgically sterile or at least 2 years post-menopausal, must have a negative serum pregnancy test at screening and a negative urine pregnancy test prior to study drug administration on Study Day 0);
16. Breastfeeding or lactating women;
17. History of alcohol or drug abuse < 1 year prior to Study Day 0;

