4.1.2 Study Reporting Period for Adverse Events

The reporting period for adverse events is the period from the signing of informed consent through Study Day 350. AEs will not be recorded for patients deemed screening failures.

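### Section 3.7 ends MI-CP151 follow-up when the MI-CP212 consent is signed, before eligibility for MI-CP212 is known, and gives no rule for signers who do not qualify

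*Protocol*

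**What the plan says.** Section 3.7 offers early termination so that a patient can move to the long-term study. The earliest point is Day 266: "Patients must complete the treatment period and follow up through study Day 266 of this study to participate in MI-CP212". The event that ends participation is the consent signature: "Patients will be considered terminated from this study upon signing the MI-CP212 informed consent form between study Day 266 and Day 350". The closing assessments for these patients are optional in wording: "If possible, patients should complete the Study Day 350 evaluations on their last study visit".

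Section 2.4.1, repeated in the Study Abstract, puts eligibility after consent: "Patients must also qualify for the long-term safety study (following written informed consent), as per the MI-CP212 protocol inclusion and exclusion criteria". Treatment in the new study depends on the result: "If patients qualify, they will receive open-label MEDI-545". The only MI-CP212 follow-up described there runs from the last MI-CP212 dose.

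Elsewhere the protocol assumes observation to Day 350. Section 3.5 follows every dosed patient however many doses were given, the only stated exception being withdrawal of consent for follow-up. Section 4.1.2 says: "The reporting period for adverse events is the period from the signing of informed consent through Study Day 350". Section 4.2.2 sets the same period for SAEs, and Section 5.4.1 summarises treatment-emergent events from first dose through Day 350.

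**The concern.** The order of events is the difficulty. Consent comes first and qualification second, but MI-CP151 closes at the first step. A patient who signs and is then found ineligible has been terminated here without having entered there. The only resumption rule in Section 3.7 concerns missing patients with whom contact is re-established.

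Safety is the primary objective, and the second half of follow-up is the period in which drug has largely cleared. For these patients the late AEs, the last viral surveillance and the last antibody samples would be missing or collected early. They would lose this data while willing to stay, and not because they had moved to another study. By contrast, Section 4.7 keeps patients who were permanently stopped from study drug, other than by withdrawal of consent, in follow-up through Day 350.

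**Working it through.** **Order of events as written**

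| Step | Source | Consequence |
|---|---|---|
| Patient reaches Day 266 | Section 3.7 | May choose MI-CP212 |
| Patient signs the MI-CP212 consent | Section 3.7 | Terminated from MI-CP151 |
| MI-CP212 criteria are checked | Abstract, Section 2.4.1 | Qualifies, or does not |
| Qualifies | Section 2.4.1 | Open-label drug, then MI-CP212 follow-up |
| Does not qualify | No section | No rule |

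**The plan's own follow-up figure.** Inputs: last dose Day 182, end of follow-up Day 350 (Section 2.4.1). 350 − 182 = 168 days; 168 / 7 = 24 weeks. This agrees with the stated 24 weeks.

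**Largest loss per patient.** Signature on Day 266: 350 − 266 = 84 days, or 12 weeks; 84 / 168 = 50% of follow-up. A signature on day d loses 350 − d days, which falls to zero at Day 350.

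**Scheduled assessments in that window (Table 5).**
- Visits after Day 266: Days 294, 322 and 350.
- Anti-drug antibodies from Day 196 on: Days 196, 238, 294 and 350, so 2 of 4 fall in the window.
- Viral surveillance from Day 196 on: Days 196, 266 and 350, so 1 of 3 falls in the window.

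**What the window represents.** Section 4.9 gives a half-life of 15 to 18 days. Day 266 is 84 days after the last dose: 84 / 15 = 5.6 half-lives (0.5^5.6 ≈ 2% of drug left) and 84 / 18 = 4.67 half-lives (0.5^4.67 ≈ 4% left). The window is mainly the drug-free period.

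**Number of patients, by assumption only.** The documents give neither a signing rate nor a failure rate. Suppose 25% to 90% of 40 patients sign and 10% to 30% of signers fail to qualify:
- Low end: 40 × 0.25 × 0.10 = 1.0
- High end: 40 × 0.90 × 0.30 = 10.8

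This gives about 1 to 11 of 40. It treats all 40 as reaching Day 266 with the option open, which overstates the base.

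**The case against.** The strongest reply is that the wording is loose and the intent is clear. The paragraph in Section 3.7 is about leaving early in order to enter MI-CP212, so a site might apply it only to patients who do enter. Section 3.5 and the reporting periods to Day 350 point the same way. This does not remove the problem: Section 3.7 is the specific rule, it names the signature as the event, and the conflict with the other sections is itself what needs correcting.

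Some softening is real. The Day 350 evaluations may be done at the last visit, and Section 3.7 makes them mandatory for discontinuations after Day 196 in general. Viral testing is already scheduled at Day 266, and an antibody sample could be drawn early. Section 4.2.2 also keeps related SAEs reportable after the study if the investigator learns of them. What stands is that assessments made near Day 266 cannot capture events over the next 84 days, and that non-serious or unrelated events fall outside the post-study provision.

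Three stronger readings are tempting and should not be drawn:
- *These patients are followed in neither study.* The MI-CP212 protocol is not at hand. Section 4.2.2 records SAEs for this study's screening failures, and MI-CP212 may or may not do the same.
- *Exclusion criterion 1 bars their return.* It rules out "Receipt of MEDI-545 in any previous clinical study or prior randomization into the trial". That governs enrolment; a patient already randomized can continue scheduled visits without being enrolled again.
- *They are the patients most likely to carry a safety signal.* The MI-CP212 criteria are not shown. Patients permanently stopped during treatment under Section 4.7 have not completed treatment, so they cannot take this route, and that section follows them to Day 350 unless they withdrew consent.

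**Conclusion.** The point holds for MI-CP151. The protocol terminates patients on a signature that precedes the eligibility decision, provides nothing for those who then do not qualify, and so contradicts its own follow-up rule and its AE, SAE and primary-endpoint windows.

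The loss per affected patient is at most 84 of 168 follow-up days with three scheduled visits, less with a later signature or if the closing evaluations are done. The range of 1 to 11 patients rests wholly on assumed rates and shows scale only. All analyses are descriptive, so no test is affected. With 6 patients initially on active drug per cohort, however, even one truncated record is noticeable in the late safety summaries. It should be corrected, as more than a point of missing detail.

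**What to change.** In Section 3.7, tie termination from MI-CP151 to actual entry into MI-CP212, for example receipt of the first MI-CP212 dose. Add that patients who sign the MI-CP212 consent but do not enter, for whatever reason, remain in MI-CP151 and complete the Table 5 visits through Day 350. Reconcile Sections 2.4.1, 3.5, 4.1.2, 4.2.2 and 5.4.1 with this, so that the reporting windows say how patients who do enter MI-CP212 before Day 350 are handled.

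The cost is a short overlap of the two protocols during MI-CP212 screening. It needs one rule, that AEs arising in that window are assigned to MI-CP151, and a check against the MI-CP212 protocol for duplicate reporting and sampling. No new patients or procedures are needed: for each patient concerned, at most three visits that Table 5 already schedules.

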5 STATISTICAL CONSIDERATIONS

5.1 General Considerations

All data will be provided in data listings sorted by treatment group and patient number. All tabular summaries will be presented by treatment group. Categorical data will be summarized by the number and percentage of patients in each category. Continuous variables will be summarized by descriptive statistics including mean, standard deviation, median, minimum, and maximum. No formal statistical tests are planned. Missing data will be treated as missing. No data will be imputed unless otherwise specified. Study Baseline values will be defined as the last valid assessment prior to the first administration of study drug. All data will be collected from screening through Study Day 350.

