5.3 Patient Populations

The patient population analyzed will include all patients who receive at least one dose of study drug.

Safety results will be analyzed in all patients who receive any study drug. Evaluability for analyses of MEDI-545 serum concentrations and PK parameters will be determined based upon the frequency and timing of the serum samples obtained. IM analysis will be performed in all patients who have received at least one dose of MEDI-545. Efficacy results will be analyzed in all randomized patients who receive any study drug.

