5.4 Study Endpoints

5.4.1 Primary Endpoints

The primary endpoints of the study are the safety and tolerability of MEDI-545, which will be assessed primarily by summarizing treatment-emergent AEs/SAEs and by assessing changes in viral cultures and titers, including oropharyngeal swabs for herpes simplex virus HSV-1 and HSV-2; vaginal swabs for HSV-1, HSV-2, and HPV; and peripheral blood test (using polymerase chain reaction tests) for EBV and cytomegalovirus. The occurrence of treatment-emergent AEs and SAEs will be summarized from the first administration of study drug through Study Day 350. AEs and SAEs occurring after administration of study drug will be coded using the current version of MedDRA and will be summarized by system organ class and preferred terms, by severity, and by relationship to study drug. AEs and SAEs will be summarized for placebo, each of the MEDI-545 dose cohorts, and for all MEDI-545 doses combined. Since patients initially randomized to placebo will receive placebo for the first 7 doses and MEDI-545 for the next 7 doses, AEs and SAEs will also be reported with respect to different treatment periods. The rate of virus detection by surveillance testing will be summarized descriptively.

No formal statistical testing will be performed to compare treatment groups. Other variables used for the safety assessments include serum chemistry, CBC with differential and platelets, and urinalysis. These variables as well as their changes from baseline will be summarized descriptively.

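### Adverse event percentages run to Day 350 over all treated patients, but rollover to MI-CP212 can end observation from Day 266, so late post-treatment events are understated

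*Protocol*

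**What the plan says.** Four parts of the protocol fix the primary safety summary.

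- Window (Section 5.4.1): "The occurrence of treatment-emergent AEs and SAEs will be summarized from the first administration of study drug through Study Day 350".
- Reporting period (Section 4.1.2): "The reporting period for adverse events is the period from the signing of informed consent through Study Day 350". No exception is made for patients who enter MI-CP212.
- Statistic (Section 5.1): "Categorical data will be summarized by the number and percentage of patients in each category". The same section adds: "Missing data will be treated as missing".
- Denominator (Section 5.3): "Safety results will be analyzed in all patients who receive any study drug".

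Section 3.7 sets the exit. The entry condition for the extension is: "Patients must complete the treatment period and follow up through study Day 266 of this study to participate in MI-CP212". The consequence is: "Patients will be considered terminated from this study upon signing the MI-CP212 informed consent form between study Day 266 and Day 350". For the final assessments it adds: "If possible, patients should complete the Study Day 350 evaluations on their last study visit".

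Section 4.7 goes the other way for patients taken off study drug for the reasons it lists, safety reasons among them. Withdrawal of consent aside, they are followed to Day 350.

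**The concern.** A crude percentage is a fair estimate of incidence by Day 350 only if nearly everyone in the denominator is watched to Day 350. Here the protocol itself plans for some patients to stop being watched up to 84 days earlier, and keeps them in the denominator as if they had been observed without an event.

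The shortfall is not random. Only patients who finished the treatment period may roll over, while those taken off drug for safety stay to Day 350. Length of follow-up therefore depends partly on how treatment went.

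What is at stake is the description of events arising late after the last dose, such as viral reactivation once exposure has fallen. Section 4.1.2 also leaves one thing open: whether an event after MI-CP212 consent but before Day 350, possibly on open-label drug, belongs to this study.

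**Working it through.** **The plan's own figures.** Tables 7 and 8 in Section 5.2 are its only numbers on AE detection and precision. All rows reproduce. For example, N = 30 at a true rate of 1.5% gives 1 − 0.985^30 = 36.5%, as printed. They refer to the period before Day 98, so they neither support nor contradict this point.

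**Inputs from the protocol.**
- Last dose: Day 182 (Section 2.4.1).
- Earliest exit: Day 266 (Section 3.7).
- End of AE window: Day 350 (Sections 4.1.2 and 5.4.1).
- Half-life: 15 to 18 days (Section 4.9).
- Planned size: 40 patients, all on MEDI-545 from Day 98 (Sections 3.4.2 and 5.2).

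**Inputs the protocol does not give, assumed over a range.**
- Rollover uptake f: 25% to 100%, with every leaver exiting on Day 266.
- True Day 350 incidence R: 10%, 20% or 50%.
- Risk q of an event confined to Days 266-350: 2%, 5% or 10%.

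**Step 1: time lost per leaver.**
- 350 − 266 = 84 days, and 84/350 = 24% of the AE window.
- 350 − 182 = 168 days after the last dose, and 84/168 = 50% of that follow-up.
- Planned person-time lost overall is f × 24%: 6%, 12%, 18% and 24% at f = 25%, 50%, 75% and 100%.

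**Step 2: effect on the Day 0-350 percentage.** With a constant hazard, incidence by Day 266 is 1 − (1 − R)^(266/350). The crude percentage is then (1 − f) × R + f × [1 − (1 − R)^(266/350)].

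For R = 10%: 266/350 = 0.76, and 1 − 0.9^0.76 = 7.70%. At f = 50% the result is 0.5 × 10% + 0.5 × 7.70% = 8.85%.

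| True R | f = 25% | f = 50% | f = 75% | f = 100% |
|---|---|---|---|---|
| 10% | 9.42% | 8.85% | 8.27% | 7.70% |
| 20% | 18.9% | 17.8% | 16.7% | 15.6% |
| 50% | 47.7% | 45.5% | 43.2% | 41.0% |

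**Step 3: events that arise only in Days 266-350.** The crude percentage shows q × (1 − f). The chance of seeing at least one among n = 40 is 1 − (1 − q(1 − f))^40.

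| q | f = 0 | f = 25% | f = 50% | f = 75% |
|---|---|---|---|---|
| 2% | 55.4% | 45.4% | 33.1% | 18.2% |
| 5% | 87.1% | 78.3% | 63.7% | 39.5% |
| 10% | 98.5% | 95.6% | 87.1% | 63.7% |

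**Step 4: where the lost time lies.** Day 266 is 266 − 182 = 84 days after the last dose, which is 84/18 = 4.7 to 84/15 = 5.6 half-lives. All lost time falls after that.

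Steps 2 and 3 are upper bounds for a given uptake, because patients may leave at any time between Day 266 and Day 350.

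**The case against.** The strongest reply is that little of importance is touched. No treatment comparison is affected: every patient receives MEDI-545 from Day 98, and no formal testing is planned. The lost time starts about five half-lives after the last dose. Viral surveillance is scheduled on Day 266 itself, so a leaver has a result there. In a trial of 40, one patient is 2.5 percentage points, so the 1.15-point shortfall in the 10% example (10% − 8.85%) is less than one patient. Section 5.4.1 also reports AEs by treatment period, and person-time denominators are often left to the statistical analysis plan.

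Most of this stands, and it makes the point minor. It does not remove it. The window, the statistic, the denominator and the exit rule are all set in the protocol, and together they give a percentage that is too low whenever anyone rolls over. Reporting by treatment period does not change who is counted as at risk after Day 266.

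A reader might infer more than the documents support:

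- **That early evaluations enter the Day 350 summaries.** Section 3.7 asks leavers to do the Day 350 evaluations at their last visit, and Section 3.5 uses one heading for the final and discontinuation visits. No section says such values are analysed as Day 350 values. The ±7-day window and the case report form entry on completion would let them be separated. They may fall under Day 350; it is not stated that they will.
- **That Day 266 is follow-up required of everyone, so the main summary should stop there.** Day 266 is only the condition for entering MI-CP212; planned follow-up is to Day 350. Stopping at Day 266 would drop the late events at issue from the main summary, and earlier withdrawals would still have unequal follow-up.
- **That late risks are generally halved.** A 5% risk shown as 2.5% requires 50% uptake, every leaver exiting on Day 266, and an event confined to the last 84 days.
- **That some dose cohorts are affected more than others.** The protocol gives no uptake by cohort.

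**Conclusion.** The point holds as a minor one. The Day 350 AE percentage, taken over all treated patients, understates late post-treatment events in proportion to the share who roll over. The bound is 24% of the AE window and 50% of post-dose follow-up per leaver. At an assumed 50% uptake on Day 266 with a constant hazard, 10% shows as 8.85% and 20% as 17.8%. An event confined to Days 266-350 is under-counted in direct proportion to uptake.

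This rests on two assumptions. Uptake is above zero, which the protocol allows but does not quantify. AE observation in this study stops when the patient is terminated from it, which is the natural reading of Section 3.7 although Section 4.1.2 does not say so. Results for Days 0-98, for dosing to Day 182 and for the first 84 days after the last dose are not affected by rollover.

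**What to change.** - Keep the Day 0-350 AE and SAE summary.
- State in Sections 4.1.2 and 5.4.1 that a rollover patient's AE observation in this study ends at MI-CP212 consent.
- Add to Section 5.4.1 an AE and SAE summary for Days 266-350, with patients or patient-days still at risk as the denominator.

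Assigning evaluations taken at rollover by actual study day can be left to the statistical analysis plan.

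The cost is one extra table and two sentences of text. No new data are needed beyond the date of MI-CP212 consent, and the main safety window is not shortened.
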